8.5.4 Additional Analysis

The relationship of the covariates listed in [Section 4.4](#) to PFS time, OS time, and tumor response rate will be explored using a logistic regression model for tumor response rate and Cox proportional hazards regression models (univariate and multivariate) for the time-to-event endpoints.

8.5.5 Sensitivity Analyses

A sensitivity analysis using the grouped survival methods of Prentice and Gloeckler may be performed on PFS time to assess the robustness of the results if there appears to be large differences in PD assessment patterns between the treatment groups.¹³

If there is substantial crossover of observation patients to pralatrexate use, a sensitivity analysis for OS may be conducted censoring such patients at the date of first pralatrexate use.

8.6 Safety Analyses

Analysis of safety will be performed on the safety analysis set. Study data will be monitored on an ongoing basis by the clinical study team including the medical monitor and the clinical drug safety team's routine activities to ensure patients' safety.

Adverse Events

The Medical Dictionary for Regulatory Activities (MedDRA) will be used to code all AEs to a system organ class (SOC) and a preferred term. Patient incidence of AEs will be tabulated by SOC, preferred term, and severity grade for all treatment-emergent AEs, serious adverse events (SAEs), treatment-related AEs, and treatment-related SAEs. Each of these outputs will include tabulation by maximum severity for each SOC and preferred term as reported by the investigator based on Common Terminology Criteria for Adverse Events (CTCAE),

Version 4.0. If an AE cannot be graded based on CTCAE, the investigator will assign a severity based on 1 = mild, 2 = moderate, 3 = severe, 4 = life threatening, and 5 = Death related to AE. Summaries of AEs that are treatment-emergent, SAEs, treatment-related AEs, and treatment-related SAEs occurring in at least 5% of the patients will be provided in descending order of frequency by SOC and preferred term.

Additional tables summarizing patient incidence (by preferred term) of the following will be generated:

- All AEs;
- SAEs;
- Treatment-related AEs;
- Treatment-related SAEs;
- Grade 3 or higher AEs;
- AEs leading to the discontinuation of pralatrexate or removal from study;
- AEs leading to dose reductions of the study drug;
- AEs with incidence $\geq 5\%$; and
- Deaths.

Adverse Events Grouped by Similar Preferred Term

Summary tables of treatment emergent, treatment-related, serious, and serious treatment-related AEs grouped by similar preferred term will be presented. For this presentation, certain similar preferred terms were identified and coded to the same preferred term in order to present the event in a uniform manner. Terms are presented in [Table 11.1](#) of Appendix 11.4 (additional preferred terms may be identified within each category during data review and added to this list).

Separate outputs will be provided for subgroups defined by age group (< 65 and ≥ 65), gender, and race (if feasible).

Detailed listings for all AEs and listings and/or narratives will be provided for serious and significant AEs and deaths (with “on-study” deaths [deaths that occur before the end of safety follow-up period] identified).

Laboratory Parameters

Laboratory parameters for hematology and blood chemistry will be summarized at baseline and last observed value. Additionally, the maximum and minimum observed post-baseline values will be summarized along with the change from baseline to the maximum observed value, minimum observed value, and last observed value. A listing of all laboratory assessments may be provided.

Incidence of laboratory abnormalities and subject incidence of Grade 3 or 4 laboratory toxicities will be presented. Summaries of hematology and serum chemistry parameters along with shifts in severity (CTCAE Version 4.0) from baseline for selected laboratory parameters will be presented.

Plasma Pharmacokinetics

Standard PK parameters will be estimated from the limited plasma sampling (eg, area under the curve [AUC], maximum concentration [C_{max}], and half-life [$t_{1/2}$]).

Population PK (POPPK) analyses will be conducted via nonlinear mixed-effects modeling to estimate POPPK parameters for pralatrexate, including typical values, inter-individual variation, and residual variability after administration of pralatrexate in the patient population, and to estimate the effects of individual-specific covariate factors (eg, demographics, disease state, etc) that may be predictive of the unexplained random variability in pralatrexate PK. In addition, the relationship between the PK of pralatrexate and response (safety and efficacy) will be explored.

Eastern Cooperative Oncology Group Performance Status

ECOG performance status scores will be summarized for each treatment group at each assessed time-point (ie, baseline and initial follow-up). The change in scores from baseline to the initial follow-up visit will also be summarized. A listing of ECOG scores will also be provided.

Protocol-specified Treatment Administration

For the Pralatrexate Arm, descriptive statistics will be calculated for total number of cycles started, the number of doses of each protocol-specified treatment, and the cumulative dose of each protocol-specified treatment. A cycle will be considered “started” if a patient receives any protocol-specified treatment during that cycle. The number and percentage of patients with modifications (including dose reductions, dose delays, or doses withheld) from the prescribed dosing of each of the protocol-specified treatments will be summarized by type of dose modification and reason for the dose modification. The overall number of dose reductions/omissions/delays per patient will also be summarized.

Electrocardiogram

A listing of all observed electrocardiogram (ECG) results will be provided.

Concomitant Medications

The number and proportion of patients receiving each reported medication will be summarized by Anatomical Therapeutic Chemical (ATC) code and preferred term for each treatment group as coded by the World Health Organization Drug (WHODRUG) dictionary. A listing of all concomitant medications by patient will also be provided.

B-symptoms and Pruritus

Presence of B-symptoms (fever, night sweats, and weight loss), along with pruritus, will be captured at baseline and will also be collected post-randomization to determine if pralatrexate has an effect on these symptoms relative to observation. Time to onset (worsening) of any,

along with time to onset of each, will be analyzed using the Cox model for the safety analysis set. Similarly, improvement in these symptoms may also be analyzed.

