### 7.2 Pralatrexate Administration

One cycle of pralatrexate therapy is 4 weeks in duration and consists of 3 weekly doses of pralatrexate IV push over 30 seconds and up to 5 minutes, with 1 week of rest. The initial dose of pralatrexate will be 30 mg/m^2/week. For patients with a body surface area (BSA) > 2 m^2, the administered dose will be calculated using a capped BSA value of 2 m^2. Pralatrexate dose reduction to 20 mg/m^2 with further reduction to 15 and 10 mg/m^2 will be allowed for defined toxicities (see [Section 7.4](#)). Pralatrexate will continue to be administered until a criterion for study treatment discontinuation is met ([Section 7.3](#)) or up to a maximum of 2 years.

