### 10.4.2 Pralatrexate Arm: Cycle 1, Doses 2-3

1. Record AEs and attribution (see <http://ctep.cancer.gov/reporting/ctc.html>). Refer to [Section 7.4](#) for the pralatrexate dose modification criteria.
2. Record current medications including compliance with vitamin supplementation.
3. Review date of previous vitamin B12 injection. Administer vitamin B12 1 mg IM q 8-10 weeks.
4. Local laboratory: Collect blood for hematology and chemistries within 1 day prior to each pralatrexate dose.
5. If the patient is not experiencing any AEs that warrant treatment modification or discontinuation, administer pralatrexate IV push over a minimum of 30 seconds up to a maximum of 5 minutes.

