### 10.4.3 Procedures for Subsequent Cycles, Doses 1-3 for a Maximum of 2 Years

Patients may continue to receive pralatrexate unless the patient experiences any of the criteria noted in protocol [Section 11.1](#).

1. Prior to each new cycle: record weight in kg and calculate BSA. The patient's weight and BSA may be assessed up to 2 days prior to the start of each cycle.
2. Prior to each new cycle: Assess and record B symptoms up to 2 days prior to the start of each cycle.
3. Record AEs and attribution (see <http://ctep.cancer.gov/reporting/ctc.html>). Refer to [Section 7.4](#) for the pralatrexate dose modification criteria.
4. Record current medications including compliance with vitamin supplementation.
5. Review date of previous vitamin B12 injection. Administer vitamin B12 1 mg IM q 8-10 weeks.
6. Local laboratory: Collect blood for hematology and chemistries (including LDH during week 1) within 1 day prior to each pralatrexate dose (see [Section 12.1](#)).
7. At cycle 2, dose 3, collect pre-injection blood sample for PK in 20 patients at select sites (see [Section 12.2.1](#)).
8. If the patient is not experiencing any AEs that warrant treatment modification or discontinuation, administer pralatrexate IV push over a minimum of 30 seconds up to a maximum of 5 minutes.
9. At cycle 2, dose 3, collect blood samples for PK in 20 patients at select sites pre-injection, end of injection, and 8 and 24 hours post-injection (see [Section 12.2.1](#)).

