### 10.5.2 Observation Arm: Week 2 of Every 4-week Period for a Maximum of 2 Years

The patient will be contacted (eg, phone call or clinic visit) week 2 of every 4-week period.

1. Record AEs and attribution (see <http://ctep.cancer.gov/reporting/ctc.html>).
- 10.5.3 Observation Arm: Every 28 days ( $\pm$  3 days) for a Maximum of 2 Years

1. Record AEs and attribution (see <http://ctep.cancer.gov/reporting/ctc.html>).
2. Assess and record B symptoms.
3. Record current medications including compliance with vitamin supplementation.
4. Review date of previous vitamin B12 injection. Administer vitamin B12 1 mg IM q 8-10 weeks.
5. Local laboratory: Collect blood for hematology and chemistries (including LDH) (see [Section 12.1](#)).

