3 STUDY DESIGN

This is an international, multi-center, randomized, Phase 3, open-label study of sequential pralatrexate versus observation in patients with previously undiagnosed PTCL who have achieved an objective response following initial treatment with CHOP-based chemotherapy.

Upon documentation of an objective response following at least 6 cycles of a designated CHOP-based chemotherapy, confirmation of histopathology by independent review, and confirmation that all eligibility criteria are met, patients will be randomized in a 2:1 ratio to either pralatrexate or observation, according to a permuted block design (block sizes of 3) stratified by response per investigator at completion of CHOP-based therapy (complete response [CR] vs partial response [PR]).

Patients randomized to the Pralatrexate Arm will receive pralatrexate as an intravenous (IV) push administration over a minimum of 30 seconds up to a maximum of 5 minutes via a patent free-flowing IV line containing normal saline (0.9% sodium chloride [NaCl]) weekly for 3 weeks (\pm 1 day at each time point) of a 4-week cycle. The initial dose of pralatrexate will be 30 mg/m² which, based on protocol-defined criteria, may be reduced to 20 mg/m² with potential further reduction to 15 mg/m² and 10 mg/m². There will be sparse sampling for pharmacokinetics (PK). Pralatrexate will continue to be administered until a criterion for study treatment discontinuation is met or up to a maximum of 2 years.

Patients randomized to the Observation Arm will remain under observation, attend clinic visits every 4 weeks, and receive a follow-up phone call from a healthcare professional during each week 2 of 4 until a criterion for study treatment discontinuation is met for a maximum of 2 years.

All patients will receive vitamin supplementation, consisting of vitamin B₁₂ 1 mg intramuscularly (IM) every (q) 8-10 weeks and folic acid 1-1.25 mg by mouth (po) once a day (qd). Vitamin supplementation will begin at least 7 days prior to the projected initiation of pralatrexate/observation and continue throughout the study until the Initial Follow-up Visit.

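### Laboratory extremes and Grade 3-4 incidence depend on the number of blood draws, which differs about threefold between arms; add a matched-draw table beside the planned ones

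*SAP*

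**What the plan says.** SAP 4.3 names two safety endpoints, and change in laboratory values is one of them. Under Laboratory Parameters, SAP 8.6 plans that "the maximum and minimum observed post-baseline values will be summarized along with the change from baseline to the maximum observed value", together with the change to the minimum and to the last value. It adds: "Incidence of laboratory abnormalities and subject incidence of Grade 3 or 4 laboratory toxicities will be presented". Protocol 15.8.3 and SAP Table 9.1 plan the same extremes, and protocol 15.8.3 the same incidences. The population is the safety analysis set, which holds both arms (SAP 6.2). SAP 8.6 does not say that laboratory results are displayed by treatment group, but that is the natural reading.

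The draw schedule differs by arm.

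- **Pralatrexate.** "One cycle of pralatrexate therapy is 4 weeks in duration and consists of 3 weekly doses of pralatrexate" (protocol 7.2). For doses 2 and 3 of cycle 1 the instruction is "Collect blood for hematology and chemistries within 1 day prior to each pralatrexate dose" (10.4.2). For later cycles it is "Collect blood for hematology and chemistries (including LDH during week 1) within 1 day prior to each pralatrexate dose" (10.4.3).
- **Observation.** Hematology and chemistry are drawn at the visit headed "Observation Arm: Every 28 days" (10.5.3), in line with SAP section 3, where these patients "attend clinic visits every 4 weeks". The week-2 contact (10.5.2) records adverse events only, and Appendix 2 shows no laboratory mark there.
- **Both arms.** One further draw at the Initial Follow-up Visit (10.7.1, 10.7.2).

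Nothing limits the extremes or incidences to visits common to both arms, adjusts for the number of draws, or says how unscheduled draws are handled.

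**The concern.** A maximum, a minimum and an ever/never Grade 3-4 flag all tend to become more extreme as more values are taken from the same patient. If one arm is sampled about three times as often, the arms will differ on these summaries even when the underlying laboratory process is identical. This is separate from any difference in how long each arm is followed.

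Safety is the only secondary objective (SAP 2.2), and a reader of the by-arm tables will take the excess on pralatrexate as toxicity. Part of it could come from the visit schedule. The authors deal with the same kind of problem for PFS: protocol 15.7.1 mentions bias from asymmetric visits, and SAP 8.5.5 offers a sensitivity analysis if progression is assessed in different patterns. Laboratory data have a larger asymmetry, built into the schedule, and no equivalent provision.

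**Working it through.** The documents give no figure for laboratory detection, so there is none to reproduce.

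**Step 1: count scheduled post-baseline draws.** SAP 5.2 defines safety baseline as the last assessment before study day 1, and assigns same-day pre-treatment values to day 0. The draw before cycle 1, dose 1 is therefore baseline. Over k four-week periods, with one Initial Follow-up draw in each arm:

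- pralatrexate: (3k − 1) + 1 = 3k
- observation: k + 1

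For k = 6 this is 18 versus 7. For k = 10, close to the 10-month median PFS assumed for observation (SAP 3.2), it is 30 versus 11. For the 2-year maximum (k = 26) it is 78 versus 27.

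**Step 2: ever-Grade-3-4 incidence with no drug effect.** Assume the same chance p per draw in both arms. The documents give no value for p. With independent draws, incidence = 1 − (1 − p)^n.

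- p = 1%, k = 6: 1 − 0.99^18 = 16.5% versus 1 − 0.99^7 = 6.8%, ratio 2.4.
- p = 1%, k = 10: 1 − 0.99^30 = 26.0% versus 1 − 0.99^11 = 10.5%, ratio 2.5.
- k = 6 over a range of p: 8.6% versus 3.4% at 0.5%, and 60.3% versus 30.2% at 5% (ratios 2.5 and 2.0).

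**Step 3: allow correlation among all draws of one patient.** Let each value be √ρ·U + √(1 − ρ)·e, with U a standard normal patient effect, e standard normal noise, and ρ the intraclass correlation (ICC). A draw is Grade 3-4 if it exceeds the 99th percentile, 2.326. Incidence is then the average over U of 1 − Φ((2.326 − √ρ·U)/√(1 − ρ))^n. The expected maximum is √(1 − ρ)·m(n), where m(n) is the expected maximum of n independent standard normals: m(18) = 1.82 and m(7) = 1.35. For k = 6, by numerical integration:

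| ICC | Incidence, 18 draws | Incidence, 7 draws | Ratio | Shift in extreme (SD) |
|---|---|---|---|---|
| 0 | 16.5% | 6.8% | 2.4 | 0.47 |
| 0.3 | 12.8% | 6.0% | 2.1 | 0.39 |
| 0.5 | 9.8% | 5.2% | 1.9 | 0.33 |
| 0.9 | 3.5% | 2.5% | 1.4 | 0.15 |

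The SD is that of a single value, between and within patients together. The minimum moves down by the same amounts.

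**Step 4: transient abnormalities.** Suppose an episode starts at random in a 28-day period and draws fall on days 1, 8 and 15 versus day 1 only. A 7-day episode is caught with probability 3 × 7/28 = 75% versus 7/28 = 25%. A 14-day episode is caught 100% versus 50% of the time. At 28 days or more both schedules catch it and the gap is gone.

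**Step 5: unequal time on study.** Observation has 7 draws over six periods. Pralatrexate reaches 7 when 3k = 7, so k = 2.3 cycles, about 40% of the observation time (2.33/6 = 39%).

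**The case against.** The strongest case is that this has little consequence. The laboratory tables are descriptive: no test, margin or decision rule depends on them, and the safety objective is to describe the safety of pralatrexate rather than to compare arms. Display by arm is inferred, and table shells are left to a separate document (SAP 9, 11.1). Pralatrexate has its own stopping rules (protocol 11.1), which may shorten its time at risk. All of this stands, and it keeps the point at the level of a cheap improvement. It does not remove it. A descriptive table can still be misread, and a shorter time on drug would cancel the effect only by accident.

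Three stronger readings are tempting and are not supported.

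- **The 3:1 schedule means nearly three times the incidence.** The pre-dose draw of cycle 1 is baseline and both arms have a follow-up draw, so the six-period ratio of draws is 18 to 7. Correlation within patients lowers the incidence ratio further.
- **All laboratory outputs are distorted.** Baseline and last-value summaries do not grow with the number of draws. Neither do severity shifts at a common time point, and Table 9.1 and protocol 15.8.3 refer to selected time points, though these are not defined. LDH is named for week 1 only on pralatrexate, so it may be sampled about equally.
- **The between-arm tables should use only the matched draws.** The draw before dose 1 of a cycle follows the rest week. A comparison based on it alone would miss mid-cycle nadirs and err in the other direction.

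**Conclusion.** The point holds for post-baseline maxima and minima, change to those extremes, and per-patient incidence of abnormalities and Grade 3-4 values. With equal follow-up and no drug effect, the plan as written gives more extreme results on pralatrexate unless abnormalities persist for about 28 days or more.

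Over six periods, at an assumed 1% per draw, the ratio of Grade 3-4 incidence is about 2.4 with independent draws, falling to 1.4 at a patient-level ICC of 0.9. The spurious shift in extremes is 0.47 to 0.15 SD. The mechanism and direction follow from the protocol's schedule. The size rests on the assumed per-draw rate, the correlation and equal follow-up, none of which the documents fix.

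A reader might infer that excess laboratory toxicity reported on pralatrexate would be an artefact. The documents do not support that: a real drug effect may be present, and the planned tables simply cannot separate it from the schedule. The PFS and OS conclusions are unaffected.

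**What to change.** In SAP 8.6 and Table 9.1, and in protocol 15.8.3 if it is amended:

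1. Keep the planned all-draw tables for both arms. State that they are displayed by arm, report the number of draws per patient by arm, and footnote the unequal schedule.
2. Add by-arm summaries of the extremes and of Grade 3-4 incidence restricted to one scheduled draw per 4-week period: the pre-dose-1 draw of each pralatrexate cycle from cycle 2, against the 28-day observation visit, plus the Initial Follow-up draw in both arms. Exclude unscheduled draws from these summaries.
3. Define the time points for the severity-shift tables so that they are common to both arms.

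With equal numbers of draws the no-effect gap disappears: at ICC 0.5 and seven draws, both arms give 5.2%. One detail needs care. A patient treated for exactly six cycles contributes 5 + 1 = 6 matched draws, against 6 + 1 = 7 on observation. At 1% and independence that leaves 5.9% versus 6.8%, a small residual in the opposite direction, so the draw counts should be shown here too.

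The cost is SAP wording and one extra table set from data already collected. The matched table understates mid-cycle nadirs, so it must be read beside the all-draw table and must not replace it. No change to the monitoring schedule is implied.

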9 LIST OF PLANNED TABLES, FIGURES, LISTINGS, AND APPENDICES

Table, listing, and figure shells will be created prior to the final analysis and will include information regarding the structure of each output. The following tables (Table 9.1), listings (Table 9.2), and figures (Table 9.3) could be provided.

Table 9.1. Planned Tables

Title	Description
Patient Disposition – FAS	Tabulates the disposition of all patients, including the number of patients randomized, the number of patients who receive protocol-specified treatment, the number of patients who were randomized and never received protocol-specified treatment. The reason for protocol-specified treatment discontinuation and the reason for study discontinuation will also be summarized. Long-term follow-up will be summarized based on the most recent assessment (alive, dead, lost to follow-up, consent withdrawn).
Baseline Demographics – FAS	Tabulates summary statistics of the demographics (gender, race, age, geriatric age group < 65, ≥ 65).
Baseline Characteristics – FAS	Tabulates baseline disease characteristics.
Patient Accountability – FAS	Tabulates the number of patients within each analysis set and the reason for exclusion from each analysis set.
Pralatrexate Administration – FAS (Pralatrexate Arm)	Summarizes the total number of cycles started, the number of doses received, duration of treatment, the cumulative dose of treatment, the number and percentage of patients with modifications by type of dose modification and reason for the dose modification. The number of dose reductions/omissions/delays per patient will also be summarized.
PFS – FAS	Summary of PFS results including median (95% CI) PFS time by treatment arm, HR (95% CI), and log-rank P value. PFS estimates (95% CIs) from K-M curves at specific time points (eg, 6-month intervals).
OS – FAS	Summary of OS results including median (95% CI) survival time by treatment arm, HR (95% CI), and log-rank P value. Survival estimates (95% CIs) from K-M curves at specific time points (eg, 6-month intervals).

Title	Description
Objective Response Rate – FAS	Summary of ORR results
Subsequent Therapy – FAS	Summary of number of patients receiving subsequent therapy, including stem-cell transplant, and timing of subsequent therapy. Also includes response status when subsequent therapy was received.
Overall Summary of Treatment Emergent AEs – Safety Analysis Set	High-level summary of treatment-emergent, serious, treatment-related, and serious treatment-related AEs. Only include treatment-emergent AEs (this applies to all AE tables).
Treatment-emergent AEs – Safety Analysis Set	Summary by SOC and preferred term for each treatment group.
Treatment-emergent AEs Grouped by Similar Preferred Term – Safety Analysis Set	Summary by preferred term for each treatment group, where selected AEs are grouped by similar preferred term as indicated in the appendix.
Treatment-emergent SAEs – Safety Analysis Set	Summary by SOC and preferred term for each treatment group.
Treatment-emergent SAEs Grouped by Similar Preferred Term – Safety Analysis Set	Summary by preferred term for each treatment group, where selected AEs are grouped by similar preferred term as indicated in the appendix.
Treatment-emergent AEs Grouped by Similar Preferred Term Leading to Treatment Discontinuation – Safety Analysis Set – Pralatrexate Arm	Summary by preferred term.
Treatment-emergent AEs by Age Group – Safety Analysis Set	Summary by SOC and preferred term for each age group (< 65, ≥ 65).
Treatment-emergent AEs by Gender – Safety Analysis Set	Summary by SOC and preferred term for each gender.
Treatment-emergent AEs by Race – Safety Analysis Set	Summary by SOC and preferred term for each race (if feasible).
Time to worsening of B-symptoms/Pruritus – Safety Analysis Set	Analysis using the Cox model of time to worsening of B-symptoms/pruritus.
Hematology – Safety Analysis Set	Summary of hematology parameters at baseline, last observed value, maximum observed value, and minimum observed value. Include change from baseline to maximum observed value, minimum observed value and last observed value.
Hematology Shift in Severity – Safety Analysis Set	Tables of shifts in severity from baseline for selected laboratory parameters and selected time points.
Serum Chemistry – Safety Analysis Set	Summary of serum chemistry parameters at baseline, last observed value, maximum observed value, and minimum observed value. Include change from baseline to maximum observed value, minimum observed value, and last observed value.

Title	Description
Chemistry Shift in Severity – Safety Analysis Set	Tables of shifts in severity from baseline for selected laboratory parameters and selected time points.
ECOG Performance Status – Safety Analysis Set	Summary of ECOG performance status results at each scheduled time-point and the change from baseline.
Concomitant Medications – Safety Analysis Set	Summary of administered concomitant medications by ATC code and preferred term.

FAS = full analysis set HR = hazard ratio SOC = system organ class
PFS = progression-free survival K-M = Kaplan Meier SAE = serious adverse event
OS = overall survival ORR = objective response rate ATC = Anatomical Therapeutic Chemical
CI = confidence interval AE = adverse event ECOG = Eastern Cooperative Oncology Group

Table 9.2. Planned Listings

Title	Description
Patient Accountability	Listing of all patients and the analysis set inclusion information.
Patient Withdrawal	Listing of all patients who withdraw from the study, including the reason for withdrawal and the time of withdrawal.
Protocol-specified Treatment Administration	Listing of all patient protocol-specified treatment administration information.
Adverse Events	Listing of all reported AEs by patient.
Serious Adverse Events	Listing of all patients with at least 1 reported SAE. Only the AEs identified as serious will be included. Listing will include patient number, SOC, and preferred term of AE, date of onset, date of resolution, CTCAE Grade, action taken, and outcome.
Deaths – Safety Analysis Set	Listing of deaths that occur within 30 days of the last dose of protocol specified treatment, including cause of death.
Adverse Events Leading to Protocol-specified Treatment Discontinuation	Listing of all patients who discontinue protocol-specified treatment due to an AE. The listing will include the AE, date of onset of the AE, date of resolution of the AE, severity of AE, and the CTCAE severity grade of the AE.
Hematology	Listing of all hematology parameters.
Serum Chemistry	Listing of all serum chemistry parameters.
Electrocardiograms	Listing of all ECG results, including heart rate, QRS, PR, QT, and QT _c intervals.
Concomitant Medications	Listing of all concomitant medications including the ATC code and preferred term.
ECOG Performance Status	Listing of ECOG performance status at each assessment.
Lesion Measurements	Listing of all lesions at each time-point, including the sum of all target lesions and change from baseline and percent change from baseline.
Efficacy Parameters	Listing of all efficacy parameters for each patient, including survival time, objective response, and PFS time.

AE = adverse event ECG = electrocardiogram PFS = progression-free survival
SAE = serious adverse event SOC = system organ class ATC = Anatomical Therapeutic Chemical
QT_c = QT interval corrected for heart rate ECOG = Eastern Cooperative Oncology Group
CTCAE = Common Terminology Criteria for Adverse Events

Table 9.3. Planned Figures

Title	Description
Progression Free Survival – FAS	Kaplan-Meier plot of PFS.
Overall Survival – FAS	Kaplan-Meier plot of OS.

FAS = full analysis set
PFS = progression-free survival
OS = overall survival

